Screening: Once the patient signs the consent form, a screening period of up to two weeks will initiate to determine the patient's eligibility for the study, prior to entering the randomization phase. Only eligible patients will enter the randomization phase.

Randomized Phase: Monthly infusions (of either B or P) will start at week 0 and continue every four weeks until week 36 (10 months) for the “randomized” phase of the study. In addition, there will be a “loading dose” at week 2 (per drug [IND] specifications). The loading dose will consist of either Belimumab or Placebo (saline) in the B or P treatment arms, respectively.

Open Label Phase: Monthly infusions (of B) will start at week 40 and continue every four weeks until week 64 (6 months) for the “open-label” phase of the study.

A comprehensive evaluation of the patient (Physical exam and history, vital signs, AEs, CBC and metabolic panel, GGT, myoglobin, pregnancy test, urinalysis, ESR, CRP, CPK, immunoglobulins, muscle and health evaluations, physician global assessment, patient self-assessments, serum level sampling) will be conducted at weeks 0, 8, 16, 24, 32, 39-40, 52, 64. A less comprehensive set of evaluations (vital signs, AEs, CBC and metabolic panel, GGT, pregnancy test) will be conducted at weeks 2, 4, 12, 20, 28, 36, 40, 44, 48, 56, 60. A detailed schedule of visits and procedures is outlined in appendix A.

A telephone follow-up conversation will also be conducted at weeks 72 and 84.

Optional Exploratory Studies

Blood based biomarker assessments and blood based RNA assessments will be performed on stored samples for consenting patients at Northwell Health only. See Appendix A (schedule of events).

b. Randomization:

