The Biostatistics Unit at the Feinstein Institute for Medical Research [BU-FIMR] will develop a web based randomization plan for the study. A randomization schema will be generated by the BU-FIMR for each participating site using the method of permuted blocks. Subjects will be randomly assigned in a 1:1 ratio to either Belimumab or Placebo, according to two stratification variables, namely, disease type (Polymyositis or Dermatomyositis) and disease severity (severe or less severe). The Biostatistics Randomization Management System (BRMS) is a secure, HIPAA-compliant, web-based application that allows investigators to randomize subjects into randomized clinical trials (RCTs) using their personal computer. The BRMS allows for multi-center, stratified, and single/double blinded RCTs, using permuted blocks. Randomization notifications are automatically sent to the PI and other authorized personnel. Using BRMS is a good way to maintain compliance in RCTs.

c. Stratification:

Randomization will be according to the two important stratification variables: disease type (Polymyositis vs. Dermatomyositis) and disease severity (severe vs less severe) and will occur at week 0 (first infusion). The number of immunosuppressive agents used by the patient over the last year (corticosteroids are not included) will be used as a surrogate of disease activity: one or less IS agent over last year versus more than 1 IS agent over last year.

d. Blinding:

This is a double-blind study; both the investigator and the patient will be blinded to the treatment assignment in the randomized phase of the trial. At the end of the 40 week randomized treatment phase all subjects will start the 20 week open label phase and therefore the drug will be dispensed in the unblinded fashion.

For each study site, there will be a designated unblinded research coordinator (URC) and a blinded research coordinator (BRC). The URC will be responsible for obtaining randomization assignments from the BU-FIMR and will oversee the preparation of infusions prior to drug administration. The BRC will be responsible for coordinating patient visits and administration or the infusion (infusion will be masked and not identifiable through any physical characteristics such as color or consistency, as the drug is of a powder form mixed in saline solution).

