- ii. If cyclophosphamide use was medically indicated after the patient's enrolment to the clinical trial, the patient will no longer receive the investigational drug, but enhanced safety monitoring will be required.
- c. A live vaccine. (Live vaccines should not be given within 30 days prior to administration or concurrently with belimumab)
- d. Any Biologic Investigational Agent (e.g., abetimus sodium, anti CD40L antibody, BG9588/ IDEC 131) or any other investigational agent not approved for sale in the country in which it is being used
 - i. 365 days Prior to Belimumab:
- e. Any Non-Biologic Investigational Agent (investigational agent applies to any drug not approved for sale in the country in which it is being used)
 - i. 30 Days Prior to Belimumab (or 5 half-lives, whichever is greater)

g. Packaging, Labeling, Preparation and Storage:

Belimumab will be supplied in a 20mL vial containing 400mg of belimumab. Belimumab should be stored at 2-8°C. After reconstitution and dilution in normal saline, the material is stable for up to 8 hours at 2-8°C, or at room temperature. The 400 mg single use vial of study agent will be reconstituted with 4.8 mL SWFI, to yield a final concentration of 80 mg/mL of belimumab.

The study agent label will contain, at a minimum, the following information:

- Product name;
- Concentration;
- Lot number;
- Storage conditions;
- Investigational drug statement; and
- Manufacturer's name and address.

The calculated dose of study agent to be administered to the subject is determined in milligrams (mg) by the assigned treatment group and the subject's body weight in kilograms (kg). The reconstituted study agent will be diluted in 250 mL normal saline for intravenous infusion. An amount of normal saline, equal to the calculated amount of product to be added, should be removed from the infusion bag prior to adding the product. After adding the reconstituted product, gently invert the bag to mix the solution. Subjects receiving placebo will receive 250mL of normal saline for intravenous infusion.

h. Data Management:

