3. Have a history of a primary immunodeficiency
4. Have a significant IgG deficiency (IgG level < 400 mg/dl) Have an IgA deficiency (IgA level < 10 mg/dL)
5. Discontinuation IS agent < 3 months prior to Screening. Including: azathioprine, methotrexate, mycophenolate mofetil, leflunomide, tacrolimus, cyclosporine, or intravenous gamma globulin [IVIG]
6. Have received Rituximab within 365 days prior to Screening.
7. Have received cyclophosphamide within 180 days prior to Screening
8. Have received treatment with:
 - a. Initiated IVIG less than 3 months prior to Screening
 - b. Pulse steroids 2 months prior to Screening
9. Have received treatment with Belimumab at any time prior to Screening
10. Have received a biologic investigational agent within 365 days prior to Screening.
11. Have received a non-biologic investigational agent within 30 days or 5 half-lives of the agent (whichever is longer) prior to Screening.
12. Have a history of an anaphylactic reaction to parenteral administration of contrast agents, human or murine proteins or monoclonal antibodies.
13. Infection history:
 - a. Currently on any suppressive therapy for a chronic infection (such as tuberculosis – including latent tuberculosis, pneumocystis, cytomegalovirus, herpes simplex virus, herpes zoster and atypical mycobacteria).

NOTE: Testing for latent TB is a standard of care for patients on immunosuppressive therapy and results will be obtained from their medical record. If no TB history is found for these patients, a Quantiferon Gold or PPD test will be performed prior to Day 0 as part of standard of care.

 - b. Hospitalization for treatment of infection within 60 days of Day 0.
 - c. Use of parenteral (IV or IM) antibiotics (antibacterials, antivirals, anti-fungals, or anti-parasitic agents) within 60 days of Day 0.
14. Have a historically positive HIV test or test positive at screening for HIV.
15. Have a history of autoimmune hepatitis
16. Hepatitis status will be obtained from patients' medical records. If unavailable, testing will be done as part of standard of care. Patients are excluded if there is evidence of chronic or active Hepatitis B infection with:
 - a. Hepatitis B:

- i. Presence of positive Hep B surface antigen independent of history of previous exposure to IVIG.
- ii. Positive hepatitis B core antibody for patients with no exposure to IVIG

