2. **Study agent should be administered by investigators/site personnel prepared** to manage infusion reactions and anaphylaxis. The infusion rate may be slowed or interrupted if the subject develops an infusion reaction. Investigators/site personnel should be aware of the risk of hypersensitivity reactions, which may present as infusion reactions, and monitor subjects closely. In the event of a serious reaction, study agent administration must be discontinued immediately and the appropriate medical therapy administered.
3. **Subjects should remain under clinical supervision for 3 hours after completion of the first 2 infusions.** In the post-marketing setting, delayed onset of symptoms of acute hypersensitivity reactions has been observed. Infusion reactions occurred more frequently on the first two infusion days and tended to decrease with subsequent infusions. Delay in the onset of acute hypersensitivity reactions has been observed and recurrence of clinically significant reactions after initial resolution of symptoms following appropriate treatment, have been observed. Therefore, patients should be monitored during and for an appropriate period of time after administration of belimumab. Subjects should remain under clinical supervision for 3 hours after completion of the first 2 infusions. Should symptoms of acute hypersensitivity occur, an extended period of monitoring may be appropriate, based on clinical judgment. This may include, but is not limited to, monitoring vital signs and observing any untoward reactions. Beyond the first 2 infusions, subjects should be monitored during and for an appropriate period of time after infusion according to the study sites' guidelines or standard operating procedure for IV infusions.
4. **Subjects should be made aware of the signs and symptoms** of delayed-type, non-acute hypersensitivity reactions that have been observed. These include symptoms such as rash, nausea, fatigue, myalgia, headache, and facial edema. Subjects should be made aware of the potential risk, the signs and symptoms of such reactions, and the importance of immediately seeking medical attention.

Safety Considerations and Adverse Events:

The investigator or site staff will be responsible for detecting, documenting and reporting events that meet the definition of an Adverse Event (AE) or Serious Adverse Event (SAE).

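### As worded, the 3-hour supervision rule is spent on saline in the placebo arm, so no fixed minimum applies at those patients' first two belimumab infusions (weeks 40 and 44)

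*Combined protocol and SAP*

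**What the plan says.** Study Drug Administration, item 3, sets one fixed observation time: "Subjects should remain under clinical supervision for 3 hours after completion of the first 2 infusions". It gives a reason: "Infusion reactions occurred more frequently on the first two infusion days and tended to decrease with subsequent infusions". It also notes that acute hypersensitivity can be delayed in onset and can recur after it has first resolved. For everything later there is no stated duration: "Beyond the first 2 infusions, subjects should be monitored during and for an appropriate period of time after infusion", with the length left to each site's own procedures for IV infusions.

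Four other places fix what a placebo patient receives and when:

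- Study Design, part g: "Subjects receiving placebo will receive 250mL of normal saline for intravenous infusion".
- Study Design, part a, Randomized Phase, on week 2: "The loading dose will consist of either Belimumab or Placebo (saline) in the B or P treatment arms, respectively".
- Study Design, part a, Open Label Phase: "Monthly infusions (of B) will start at week 40 and continue every four weeks", through week 64.
- Exclusion Criteria, item 9, rules out anyone who would "Have received treatment with Belimumab at any time prior to Screening".

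On the change of phase, Study Design, part d (Blinding), says that "all subjects will start the 20 week open label phase and therefore the drug will be dispensed in the unblinded fashion". It does not mention supervision time, and it does not say that patients' earlier assignments are disclosed at that point. The notes to Appendix A refer to standard-of-care monitoring at infusion visits and give no duration.

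**The concern.** The rule counts infusions, but the risk it addresses comes with exposure to belimumab. In the belimumab arm the two coincide. In the placebo arm they are 40 weeks apart: the 3-hour period falls on two saline infusions, and first exposure to the antibody falls under the clause that leaves observation time to the site. A site that follows the text exactly could use a shorter local observation time at the infusions that item 3 itself identifies as more prone to reactions. Serious hypersensitivity and infusion reactions come first in the protocol's list of adverse events of special interest, so the point bears on a risk the sponsor has already singled out. It concerns patient safety and affects no endpoint or efficacy analysis.

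**Working it through.** The plan gives no figure to reproduce here. The check is a count of infusions from the schedule, compared with the wording of item 3.

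**Inputs**

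- Randomised phase: every 4 weeks from week 0 to week 36, plus week 2 (Study Design, part a).
- Open-label phase: every 4 weeks from week 40 to week 64 (same section).
- Planned arm size: 15 per arm, 30 in total (Sample Size Considerations).
- Supervision rule: 3 hours, first 2 infusions (Study Drug Administration, item 3).

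**Step 1. Position of the first belimumab infusions in the placebo arm**

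- Randomised phase: (36 − 0)/4 + 1 = 10 infusions, plus week 2 = 11.
- Open-label phase: (64 − 40)/4 + 1 = 7 infusions. Total 11 + 7 = 18.
- Week 40 is infusion 11 + 1 = 12, and week 44 is infusion 13. Both come after the first 2, so the site-practice clause governs them.

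Item 1 of the same section spaces the first three doses two weeks apart, which might suggest a week 42 dose after crossover. Neither Study Design, part a, nor Appendix A has a week 42 visit, so weeks 40 and 44 are the right pair.

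**Step 2. What the literal rule covers, on planned numbers**

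| | Belimumab arm | Placebo arm | Total |
|---|---|---|---|
| Infusions with the 3-hour period (weeks 0 and 2) | 15 × 2 = 30, belimumab | 15 × 2 = 30, saline | 60 |
| First two belimumab infusions | 30 (weeks 0 and 2) | 30 (weeks 40 and 44) | 60 |
| Of these, with the 3-hour period | 30 | 0 | 30 |

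The rule thus covers 2 of 2 first belimumab infusions for a belimumab-arm patient and 0 of 2 for a placebo-arm patient.

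**Step 3. Allowing for losses before week 40**

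The documents give no rate for placebo patients leaving before week 40. Assuming 0-20%, the number still in the trial is 15 × 0.80 = 12 up to 15 patients, which is 24 to 30 infusions.

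**Step 4. Does any other text restart the rule?**

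The Open Label Phase text, the Blinding section and the Appendix A notes were each read for this, and none does. One sentence in item 3 names belimumab when it calls for monitoring after administration, but it sets no minimum time.

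**The case against.** The strongest reply is that item 3 means belimumab infusions. Its rationale is drawn from belimumab's post-marketing record, and the second statement of the rule directly follows a sentence about monitoring after belimumab. Item 1 of the section speaks of a 10 mg/kg dose, which saline cannot have. On that reading weeks 40 and 44 are already covered. The reading is plausible, but the text never states it, and elsewhere the protocol counts infusions whatever they contain: the Randomized Phase text speaks of infusions of either product, and Statistical Methods defines an evaluable subject by the first five planned infusions in either arm. Nor does the protocol tell anyone to identify former placebo patients at week 40 and start a second 3-hour period for them. If the sponsor intends this reading, it needs to be written down.

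Three smaller points stand as limits on the finding:

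- The rule is phrased as a recommendation (should), so the comparison is between a recommended 3 hours and a recommended but unspecified period.
- Other safeguards continue at weeks 40 and 44: personnel able to manage anaphylaxis, monitoring during and after the infusion, longer observation if symptoms appear, and vital signs before and after. Whether any patient would be watched for less than 3 hours depends on site procedures that are not in the documents, and the documents give no reaction rate from which to estimate harm.
- Fifteen is the planned arm size for evaluable patients. Replacement of drop-outs, or incomplete blocks within site and stratum, could put somewhat more than 15 on placebo.

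None of these changes the gap or its remedy.

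**Conclusion.** The concern holds. As item 3 is worded, the 3-hour period covers none of a placebo patient's first two belimumab infusions. On planned numbers that is 15 patients and 30 of the trial's 60 first-or-second belimumab infusions, or 12 to 15 patients and 24 to 30 infusions if 0-20% of the placebo arm leaves before week 40. This rests on the literal reading of the rule, the planned arm size and the assumed range of losses. Confidence is medium because the belimumab-specific reading cannot be excluded. What lapses is the specified 3 hours, not monitoring as such. The sponsor should correct it: the change is cheap, and the affected infusions are those for which the rule's own rationale was written.

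**What to change.** Amend item 3 so that all subjects, whatever their original assignment, are supervised for 3 hours after the first two infusions of the randomised phase (weeks 0 and 2) and again after the first two open-label infusions actually received (planned for weeks 40 and 44). Tying the second period to infusions received covers missed visits. Reword the opening of the later-infusions clause so that it applies to all other infusions, and add a footnote at weeks 0, 2, 40 and 44 in Appendix A. Coverage of placebo patients' first two belimumab infusions then rises from 0 of 2 to 2 of 2. Because the rule is the same for everyone, it discloses no one's earlier assignment.

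The cost is the wording change plus, on planned numbers, at most 30 × 2 × 3 = 180 hours of observation, less whatever post-infusion time sites already provide. Up to 15 × 2 × 3 = 90 of those hours fall on patients who have been on belimumab since week 0 and do not need them; that is the price of leaving earlier assignments undisclosed.

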Adverse Event and Serious Adverse Event Reporting:

The investigator or site staffs are responsible for detecting, documenting and reporting events that meet the definition of an AE or SAE.

- All AEs must be reported to the coordinating site.
- All SAEs must be reported to the coordinating site and local IRB within 24 hours. The coordinating site will report all SAEs to the coordinating site's IRB, the sponsor and the FDA.

All AEs and SAEs must be reported on an Adverse Event/Serious Adverse Event case report form. The study investigator is responsible for noting the relationship of the event to the study drug, the severity of the drug (criteria for grading toxicity will be based on NCI's Common Terminology Criteria for Adverse Events version 4.03), the actions taken with the investigational product, and any other medications used to treat the adverse event or serious adverse event.

Time Period and Frequency of Detecting AEs and SAEs:

The investigator or site staffs are responsible for detecting, documenting and reporting events that meet the definition of an AE or SAE. AEs will be collected from the start of the study treatment until the end of the study. SAEs will be collected from the start of the study treatment until the end of the study. All SAEs will be reported to the coordinating site, sponsor and IRB within 24 hours.

NOTE: Any SAEs assessed as **related** to study participation (e.g. study treatment, protocol-mandated procedures, invasive tests, or change in existing therapy) or related to a GSK concomitant medication, will be recorded from the time a subject consents to participate in the study up to and including any follow up contact.

Study Procedures & Assessments:

The following assessments will occur throughout the study (see Appendix A for schedule of events):

- Informed Consent and Inclusion/Exclusion Criteria will be assessed at the screening visit. After a subject signs the informed consent they will enter the screening period (≤ 2 weeks) and have eligibility determined prior to Day 0.

Laboratory assessments:

- a. CBC, Comprehensive metabolic, GGT, ESR, CRP, CPK, serum myoglobin, immunoglobulins, urinalysis and urine pregnancy test will be collected at screening.
- b. CBC, Comprehensive metabolic, GGT, ESR, CRP, CPK, serum myoglobin, immunoglobulins and urinalysis **collected within 2 weeks prior to screening can be used** for eligibility determination.

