- c. Testing for latent TB is a standard of care for patients on immunosuppressive therapy and results will be obtained **from their medical record**. If no TB history is found for these patients, a Quantiferon Gold or PPD test will be performed prior to Day 0 as part of **standard of care**.
- d. Hepatitis status will be obtained from patients' **medical records**. If unavailable, testing will be done as part of **standard of care** during the screening period.
- Vital signs will be assessed prior to infusion and after the infusion at every visit.
- Adverse events assessed at every visit. Criteria for grading toxicity will be based on NCI's Common Terminology Criteria for Adverse Events version 4.03. (Adverse Events/Serious Adverse Events (CTCAE Version 4.03)
- A Physical Exam will be performed by the Investigator at Screening, Day 0, Week 8, 16, 24, 32, 40, 52, & 64.
- Urine Pregnancy testing for WOCBP will be conducted at each study visit and 16 weeks after last dose. Urine pregnancy tests must be completed < 7 days prior to the first dose and prior to each IP administration, but not more than once a month. In the event that the urine pregnancy test is indeterminate, a serum pregnancy test will be done.
- Laboratory tests: CBC, Comprehensive metabolic, GGT, ESR, CRP, CPK, myoglobin and urinalysis will be collected at every study visit and follow up week 64.
- An immunoglobulin panel will be collected and assessed at: Screening, Week 40, & 64. Under special circumstances monthly IgG monitoring may be required (see Section: Study Design, part f) and will be performed as part of standard of care.
- Flow Cytometry and RNA-seq are collected at: Day 0, Week 8, 40, Week 48, & Week 60 or 64.
- Cytokine levels (and optional research Northwell only) will be measured at: Day 0, Week 40, & Week 60 or Week 64.
- Patients should be clinically assessed for suicidal ideation and/or behaviour at each study visit using the Columbia Suicide Severity Scale (C-SSRS)
- The Investigator will complete a Physician Global Assessment (PGA, a VAS scale of 10cm), Manual Muscle Test-8 (MMT-8), & Myositis Disease Activity Assessment Tool (MDAAT) at Screening, Day 0, Week 8, 16, 24, 32, 40, 52, & 64
- The Investigator will complete a Muscle Damage Index (MDI) assessment at Screening, Week 40 and Week 64
- Health Assessment Questionnaire (HAQ) and Patient Global Assessment (PGA, a VAS scale of 10cm) will be completed by subjects at Screening, Day 0, Week 8, 16, 24, 32, 40, 52, & 64

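### The once-a-month clause on urine pregnancy tests, read as a cap, conflicts with the week 2 test in the visit schedule, and no text says which rule prevails

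*Combined protocol and SAP*

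**What the plan says.** The bullet in Study Procedures & Assessments opens with a visit rule: "Urine Pregnancy testing for WOCBP will be conducted at each study visit and 16 weeks after last dose". Its next sentence adds two timing rules. For the first dose, "Urine pregnancy tests must be completed < 7 days prior to the first dose". For later doses, tests are due "prior to each IP administration, but not more than once a month".

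Elsewhere the protocol ties testing to visits:

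- Study Design, a. Study Procedures and Schedule, lists the shorter set of evaluations as "vital signs, AEs, CBC and metabolic panel, GGT, pregnancy test) will be conducted at weeks 2, 4, 12", and onwards. Week 2 is named in running text.
- The Pregnancy section and the pregnancy-test footnote to Appendix A both call for a test at every study visit. Appendix A has a week 2 column.
- A test is also due at screening: "urinalysis and urine pregnancy test will be collected at screening". Screening is short: "a screening period of up to two weeks will initiate".

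The assessments section opens with a pointer to the schedule: "The following assessments will occur throughout the study (see Appendix A for schedule of events".

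**The concern.** The second infusion, the loading dose, comes two weeks after the first. A site working from the visit schedule tests before it. A site that takes the once-a-month clause as a limit has a stated ground for omitting that test and dosing on the previous one. Either course departs from one of the protocol's statements on a strict reading, so either could be logged as a deviation.

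At stake is one fetal-safety check early in treatment. No efficacy endpoint, power figure or analysis method depends on it.

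**Working it through.** The plan gives no count of tests or age of tests to reproduce, so this is interval arithmetic on the stated schedule.

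**Inputs**

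- Infusion weeks (Study Design a.): 0, 2, 4, 8, 12, ..., 36 in the randomized phase (11) and 40, 44, ..., 64 in the open-label phase (7). Total 11 + 7 = 18.
- Weeks with a scheduled pregnancy test (Study Design a.): the comprehensive list has 8 entries and the shorter list has 11. Counting 39-40 as week 40, that week is in both, so there are 8 + 11 − 1 = 18 distinct weeks. They are the same 18 weeks as the infusions.
- Length of a month: 28 days, from "Monthly infusions (of either B or P) will start at week 0 and continue every four weeks until week 36".
- Day of the first-dose test: Day −6 to Day 0, from the rule of less than 7 days.

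**Step 1: gaps between scheduled tests.** Week 0 to 2 is 2 × 7 = 14 days, and week 2 to 4 is also 14 days. From week 4 on, each gap is 4 × 7 = 28 days. Only the tests around week 2 are closer together than a four-week month.

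**Step 2: apply the clause as a cap.** A test on day d is allowed only if d − (day of the last test) ≥ 28.

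| First test | Week 2 (day 14) | Week 4 (day 28) | Later visits |
|---|---|---|---|
| Day 0 | 14 − 0 = 14, barred | 28 − 0 = 28, allowed | 28 each, allowed |
| Day −6 | 14 − (−6) = 20, barred | 28 − (−6) = 34, allowed | 28 each, allowed |

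The capped rule therefore leaves 17 of 18 infusions with a test of their own and 1 of 18 (week 2) resting on a test 14 to 20 days old. The visit schedule covers all 18.

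**Step 3: screening and Day 0.** These are at most 14 days apart, which is less than 28, so testing at both also exceeds a literal cap. If the screening test is within six days of the first dose, it meets the first-dose rule and the cap would bar the Day 0 test. If it is earlier, the first-dose rule itself forces a second test inside the month. Either way the first dose is covered by a test less than 7 days old.

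**Step 4: week 39.** The lists give both 39-40 and 40. If week 39 is a separate visit, it falls (39 − 36) × 7 = 21 days after week 36, and the cap would bar a test there. No infusion is given at week 39, and week 40 is 28 days after week 36, so the count of 1 in 18 stands.

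**The case against.** The clause sits in a sentence about what must be done. It can be read as limiting that obligation: tests tied to dosing are not required more often than monthly. The separate every-visit rule then supplies the week 2 test and nothing conflicts. Four statements favour testing at every visit, including the opening of the same bullet. Appendix A is named as the detailed schedule in the caption of the study flowchart, in Study Design a. and at the head of the assessments section. On this view, different practice between sites is conjecture.

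Much of this stands. A reader might infer that the two rules cannot both be followed on any reading. The documents do not support that, because the narrower reading is available and the weight of the text is on its side. What does not stand is that the matter is settled. The pointers to Appendix A say where the schedule is, not that it overrides the clause, and nothing marks the week 2 dose as either exempt or included.

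A reader might also take a month as 30 or 31 days and infer that 9 of 18 infusions would lack their own test. The protocol equates monthly infusions with every four weeks and states no 30- or 31-day rule, so that figure should not be used.

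**Conclusion.** This is a minor inconsistency in an operative safety rule and worth correcting. Its size is 1 of 18 infusions (week 2), given on a test 14 to 20 days old, and only at a site that applies the clause as a cap. That rests on a four-week month and on a first-dose test between Day −6 and Day 0.

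The safety impact is small. The woman has a recent negative test, and Inclusion Criteria item 11 requires abstinence or two contraceptive methods. That placebo patients receive saline at week 2 is little comfort, since the belimumab arm does receive drug then. The documents do not give the number of women of childbearing potential, so the number of doses affected cannot be stated. The primary endpoint, sample size and analysis are untouched.

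**What to change.** In the urine pregnancy testing bullet of Study Procedures & Assessments, strike everything after the comma in "prior to each IP administration, but not more than once a month". The sentence then keeps the first-dose limit and the requirement for a test before each administration. It agrees with Study Design a., the Pregnancy section and the Appendix A footnote.

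The cost is one clause in the protocol. No test is added beyond those already scheduled. Compared with a literal cap applied to the infusion visits, the change restores the week 2 test for each woman of childbearing potential and, where screening falls shortly before dosing, the Day 0 test as well.
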